6. DEFINITION OF STUDY OUTCOMES

6.1 Poor Neurological outcome

Defined as a DRS score > 5 (See Appendix 8).

6.2 Bleeding

Defined as TIMI minor or major (See Appendix 7).

6.3 Stroke

A neurologic injury occurring as a result of a disease process involving one or more of the blood vessels of the brain, i.e. atherosclerosis, dissection, thrombus, embolism, decreased perfusion pressure resulting in inadequate blood flow, vessel rupture associated with intracranial haemorrhage. Strokes will be classified as hemorrhagic or non-hemorrhagic with duration > 24 hrs.

6.4 Cardiogenic Shock

Systolic blood pressure < 80 mm Hg not responding to fluid expansion, and requiring the use of intravenous inotropic support or the use of intra-aortic balloon counterpulsation.

6.5 Stent Thrombosis According to Academic Research Consortium (ARC)

The Academic Research Consortium (ARC) of academic investigators, regulators, and industry representatives has proposed definitions to serve as standard criteria for stent thrombosis for the comparison of event rates across different trials and studies.¹¹

Stent thrombosis was classified as:

- 1) Acute if it occurred within 24 hours after the index procedure,
- 2) Subacute if it occurred between 1 and 30 days after,
- 3) Late if it occurred between 31 days and 1 year after, and
- 4) Very late if it occurred more than 1 year after the procedure.

Stent thrombosis was then classified as definite, probable, or possible.

Definite stent thrombosis required the presence of an acute coronary syndrome with angiographic or autopsy evidence of thrombus or occlusion.

Probable stent thrombosis included unexplained deaths within 30 days after the procedure or acute myocardial infarction involving the target-vessel territory without angiographic confirmation.

Possible stent thrombosis included all unexplained deaths occurring at least 30 days after the procedure.

Intervening target lesion revascularization was defined as any repeated percutaneous revascularization of the stented segment, including the 5-mm proximal and distal margins that preceded stent thrombosis.

6.6 PCI Procedural Success

PCI procedural success is defined as the achievement of TIMI grade 3 flow with < 30% residual stenosis by visual estimate.

7. STATISTICAL AND ANALYTICAL METHODS

All analyses on the primary outcome and its components will be performed on an intention-to-treat. The primary outcome will be compared between treatment arms using a significance level of 5% and a power of 80%. Secondary outcomes will be examined using parametric or non-parametric statistics as appropriate for the scale of measurement of the dependent variables. Analyses will be conducted using SAS.

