3.6 Statistical Analyses

3.6.1 Sample size

A total of 340 patients will be required to detect an absolute 15% risk reduction (30% relative risk reduction) in the primary outcome based on an anticipated event rate of 50% in the mild hypothermia group and of 35% in the moderate hypothermia group using a chi-square test for comparing proportions with alpha set of 0.05 and a power of 80%.

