4.7 Pre-specified subgroups

The following pre-specified subgroups will be analyzed at the end of the study:

1. Ventricular tachycardia or ventricular fibrillation as initial rhythm
2. ST segment elevation myocardial infarction as index event
3. Patients taken to the cardiac catheterization laboratory within 12 hrs of the cardiac arrest event
4. Patients undergoing percutaneous coronary intervention
5. Patients age >75yrs

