7.1 Hypothesis Testing

Primary and secondary efficacy parameters will be evaluated for treatment-associated differences between the two groups. The null hypothesis states that there will be no between treatment difference. The

alternate hypothesis states that moderate TH will be significantly more effective than the mild TH at reducing the number of primary outcome events at six months.

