7.3 Comparability of Patient Groups

Descriptive statistics will be used to evaluate the comparability of patients randomized to either group with respect to age, gender, cardiovascular history, functional capacity, medications and interventions administered in hospital, and course in hospital.

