8. SAMPLE SIZE

8.1 Sample Size

Outcome measures for all randomized patients will be analyzed in an intention-to-treat analysis. The primary outcome of our study will be a composite of 1) death or 2) poor neurologic outcome, at 6 months. Based on our review of the literature and our own cardiac arrest database we estimate an event rate of 50% in the mild TH group. To detect a 30% relative risk reduction with 80% power and a type I error of 5% will require a sample size of 340 patients (170 per temperature group).

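### The primary comparison names no covariate and leaves out age, a baseline value already needed for other analyses; this forgoes some efficiency but causes neither bias nor a power shortfall.

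*Combined protocol and SAP*

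**What the plan says.** Section 7 states that "The primary outcome will be compared between treatment arms using a significance level of 5% and a power of 80"%, on an intention-to-treat basis. It gives no test statistic, model or covariate. A method appears only in 3.6.1, where the trial is sized "using a chi-square test for comparing proportions".

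Age comes up in three places. It is an eligibility condition (3.2, 4.2.2 and the screening form in Appendix 2). Section 7.3 will describe the arms "with respect to age, gender, cardiovascular history, functional capacity" and further items, and states no consequence if they differ. Section 4.7 lists "Patients age >75yrs" among five subgroups. The last two uses need the age value itself, so it has to be recorded for everyone.

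Section 4.2.4 stratifies randomization by initial rhythm alone. Rhythm is the only variable that the plan describes as prognostically important. No section adjusts the primary comparison for rhythm, age or anything else.

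**The concern.** If age predicts death or a poor DRS score at six months, an analysis without it carries outcome variation that it could have removed. Randomization does not balance age by design, and an analysis by rhythm strata would not remove its effect either. Two things follow: a somewhat less powerful test than the same 340 patients could give, and an estimate that moves with whatever age imbalance chance produces.

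There is also a pre-specification gap. Section 7.3 will look at age balance but neither provides for adjustment nor rules it out. It lists age beside items that arise after randomization, such as in-hospital treatment and course. If an imbalance appears, any adjusted result would be post hoc, and nothing in the plan says which variables would be legitimate covariates.

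**Working it through.** **1. The plan's own figure.** Inputs from 3.6.1 and 8.1: "anticipated event rate of 50% in the mild hypothermia group and of 35% in the moderate hypothermia group", alpha 0.05, power 80%, 170 per group. With pooled variance, two-sided, no continuity correction:

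n per arm = [1.960·√(2·0.425·0.575) + 0.842·√(0.5·0.5 + 0.35·0.65)]² / 0.15² = (1.370 + 0.582)² / 0.0225 ≈ 169.3, rounded up to 170, so 340 in total. This matches exactly.

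Power at 170 per arm: Φ[(0.15·√170 − 1.370) / 0.691] = Φ(0.847) = 80.2%. Section 7.1 words the alternative in one direction, but a one-sided calculation would give 268, so the sizing is two-sided.

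**2. Precision of the unadjusted estimate.** SE = √[(0.25 + 0.2275)/170] = 5.3 points. The 95% half-width is 1.96 × 5.3 ≈ 10.4 points.

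**3. Assumptions that the documents do not supply.** Odds ratio per SD of age from 1.0 to 2.0; 60% VT/VF; rhythm odds ratio 3 or 5. Marginal risks are held at 50% and 35%, with 1:1 allocation within rhythm.

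**4. Power gain from adding age to arm + rhythm.** Logistic model, N = 340, 8,000 simulated trials per scenario:

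| OR per SD of age | Rhythm OR 3 | Rhythm OR 5 |
|---|---|---|
| 1.35 | 82.7 → 83.8% | 85.2 → 86.0% |
| 1.6 | 82.3 → 84.2% | 85.5 → 86.7% |
| 2.0 | 82.4 → 85.5% | 85.1 → 87.9% |

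A repeat with 6,000 trials per scenario gave gains of 0.4 to 0.9, 1.7 to 2.3 and about 3.5 points on the three rows, and no gain at OR 1.0. Each power figure has a Monte Carlo SE of about 0.5 point. The gain is therefore about 0 to 3.5 points.

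With age as the only covariate (rhythm not modelled), the variance of the risk difference falls to about 1.00, 0.99, 0.96 and 0.91 of the unadjusted value at OR 1.0, 1.25, 1.5 and 2.0. Equal precision would then need about 340, 337, 327 and 310 patients.

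**5. Effect of chance age imbalance.** The between-arm difference in mean age has an SD of 2/√340 = 0.108 age SDs. The 95% shift in the unadjusted risk difference is 1.96 × 0.108 × ln(OR) × m, where m is the mean of p(1−p) given rhythm and age, averaged over the arms.

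| OR per SD | m (rhythm OR 5 to 3) | 95% shift, points |
|---|---|---|
| 1.0 | any | 0 |
| 1.35 | 0.203 to 0.219 | ±1.3 to 1.4 |
| 1.6 | 0.200 to 0.214 | ±2.0 to 2.1 |
| 2.0 | 0.193 to 0.205 | ±2.8 to 3.0 |

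Using the marginal value instead, m = (0.25 + 0.2275)/2 ≈ 0.24, would give ±1.5, ±2.4 and ±3.5. That is too large, because p(1−p) averages lower once rhythm and age are accounted for.

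As a share of the unadjusted variance, the shift accounts for (1.4/1.96)²/5.3² ≈ 2% at OR 1.35 and (3.0/1.96)²/5.3² ≈ 8% at OR 2.0.

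**6. Validity of the unadjusted test.** In simulations with age as the only covariate (OR 1.0 to 2.5 per SD, 6,000 trials each), the unadjusted estimate was unbiased and its two-sided type I error was 4.4 to 5.0%.

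**The case against.** The strongest reply is that an unadjusted comparison of two proportions is sound here. It is unbiased, holds its error rate, and is the test for which 340 was calculated. A reader might infer that the trial needs age adjustment to reach its power. It does not: the planned 80% is met without it. A reader might also infer that age imbalance would bias the result. It would not: such imbalance is part of the random error that the ±10.4-point interval already expresses.

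A third tempting inference is that the plan itself treats age as an important predictor. It does not say so. Age is one entry in a descriptive list and one of five subgroups, and a subgroup concerns a possible difference in treatment effect, not prognostic strength. All of this stands. So does the remark that rhythm, the stratification factor, has the better documented claim to be in the model, and that naming any single primary analysis, even an unadjusted one, would stop a choice made after seeing the data.

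What the reply does not remove is that section 7 names no analysis at all. When that gap is filled, a baseline value already needed for 4.7 and 7.3 can be used at almost no cost. If age turns out to be unrelated to outcome, the simulated power loss from including it is negligible.

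**Conclusion.** The point holds as one of forgone efficiency and incomplete pre-specification. The gain from age on top of rhythm is about 0 to 3.5 power points, and the chance shift that it would remove is 0 to about ±3 points against a 15-point target. Both ranges rest on an assumed odds ratio of 1.0 to 2.0 per SD of age and on assumed rhythm mix and strength. The documents supply none of these, so the loss cannot be stated as a fact or narrowed further. Invalidity, bias or an underpowered design should not be read into it. The change is worth making because it is cheap, not because the trial fails without it.

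**What to change.** In section 7, name the primary analysis: a logistic model with arm, initial rhythm (the stratification factor) and age as a continuous term. Report the standardized (marginal) risk difference with a 95% CI by the delta method or bootstrap, stating which, so that the target remains the absolute difference used for sizing. Take the primary p-value from that same analysis. Keep the unadjusted chi-square as a supporting analysis. In 7.3, add that the baseline comparison is descriptive and does not change the covariate set, and that items arising after randomization are not used as covariates. Settle this before outcomes are compared by arm.

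The cost is a paragraph of analysis text. The sample size and conduct do not change, and the age value is already required by 4.7 and 7.3. The small downside is that the headline estimate comes from a model rather than a raw two-by-two table.

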7.1 Hypothesis Testing

Primary and secondary efficacy parameters will be evaluated for treatment-associated differences between the two groups. The null hypothesis states that there will be no between treatment difference. The

alternate hypothesis states that moderate TH will be significantly more effective than the mild TH at reducing the number of primary outcome events at six months.

7.2 Efficacy Analysis

All participants, who receive study treatment, will be included in the analyses according to their initial randomization group, i.e. intention to treat analysis. No interim analysis is planned.

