4.2.4 Randomization

Randomization will be performed in a 1:1 fashion by sealed opaque envelopes and treatment assigned by random number generation done in blocks. Patients will be randomized immediately following insertion of the endovascular cooling catheter. Because patients with ventricular tachycardia (VT) or ventricular fibrillation (VF) have better survival than other rhythms¹⁰ patients will be stratified based on their initial rhythm. Patients with an initial rhythm of either VT or VF will be randomized from a different series of envelopes than patients with an initial rhythm of asystole or pulseless electrical activity (PEA). The two different series of randomization

envelopes will be identifiable and differentiable by coding (ie. VT/VF randomization codes will begin by the number 1, while randomization codes for asystole/PEA will begin by the number 2). This will ensure balancing in the groups in this important prognostic factor.

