4.3 Interventions

Eligible patients will be randomized to mild TH (goal cooling temperature of 34°C) or moderate TH (goal cooling temperature of 31°C). The rate of cooling to the signed temperature after randomization will be on the basis of as fast as technically feasible by the device. Cooling will be performed via an endovascular cooling device (ZOLL Medical Corporation, Chelmsford, MA) inserted via the femoral vein into the inferior vena cava either in the cardiac catheterization laboratory or in the coronary care unit. Our current practice is to target 33°C with the identical protocol. Paramedics and transferring facilities will be encouraged to initiate hypothermia with ice packs as soon as possible (prior to arrival at the University of Ottawa Heart Institute). This is done by placing ice packs to the neck, groin and axilla.

Upon presentation to the University of Ottawa Heart Institute, patients may be taken to the cardiac catheterization laboratory at the discretion of the treating team for coronary angiography and/or insertion of a mechanical support device (intra-aortic balloon pump).

All patients will be sedated, intubated and ventilated. The University of Ottawa Heart Institute standard cooling protocol will be used to implement sedation, analgesia and neuromuscular blockade. Paralytic agents will be used during the cooling process to inhibit shivering. All of these medications and monitoring are currently the standard of care. The temperature will be recorded via the ZOLL catheter. Patients will have nasopharyngeal and bladder temperature probes inserted to correlate with temperatures monitored intravascularly.

Patients who present to the Ottawa Heart Institute with body temperatures $<34^{\circ}\text{C}$ can still be randomized to one of the groups. The temperature will be adjusted with the endovascular cooling device according to the randomly assigned temperature. Note that the device is capable at cooling or warming to the set target temperature.

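### Section 7.2 can be read as limiting the intention-to-treat set to treated participants, whereas section 8.1 analyses all randomized patients; one set should be named

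*Combined protocol and SAP*

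**What the plan says.** Four statements in the combined protocol and SAP bear on who is analysed.

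- Section 7.2, which covers efficacy, states: "All participants, who receive study treatment, will be included in the analyses according to their initial randomization group, i.e. intention to treat analysis".
- Section 8.1 (Sample Size): "Outcome measures for all randomized patients will be analyzed in an intention-to-treat analysis".
- Section 7 (opening paragraph): "All analyses on the primary outcome and its components will be performed on an intention-to-treat". The set is not defined there.
- Section 7.3 (Comparability of Patient Groups): "Descriptive statistics will be used to evaluate the comparability of patients randomized to either group".

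Section 7.1 says "Primary and secondary efficacy parameters will be evaluated for treatment-associated differences between the two groups", so the efficacy analysis of section 7.2 appears to cover secondary as well as primary outcomes.

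Two further statements fix the order of events. Section 4.2.4: "Patients will be randomized immediately following insertion of the endovascular cooling catheter". Section 4.3: "The rate of cooling to the signed temperature after randomization will be on the basis of as fast as technically feasible by the device". Assigned cooling therefore starts after allocation.

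**The concern.** Sections 7.2 and 8.1 both use the intention-to-treat label, but on one reading they attach it to different sets of patients. If receipt of study treatment is a condition of entry, a patient who is randomized and dies or is withdrawn before assigned cooling starts is left out under section 7.2 and kept under section 8.1. Death is a component of the primary outcome, so leaving out such a patient can remove a primary event after allocation. That is the selection intention to treat is meant to prevent.

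The condition would also be hard to apply, because the plan does not define receipt of study treatment. Section 4.3 allows ice-pack cooling before arrival and allows randomization of patients who arrive below 34°C. A patient with the catheter in place but no active temperature control could be classed either way. On the restrictive reading, the baseline comparison in section 7.3 (patients randomized) and the efficacy comparison could also rest on different patients.

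**Working it through.** **1. The plan's own figure.** Inputs: "we estimate an event rate of 50% in the mild TH group" (section 8.1); 35% in the moderate group, chi-square test, alpha 0.05, power 80% (section 3.6.1); 1:1 allocation (section 4.2.4). Sidedness is not stated; two-sided is assumed. With mean rate 0.425:

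n per arm = [1.960·√(2·0.425·0.575) + 0.842·√(0.50·0.50 + 0.35·0.65)]² / 0.15² = (1.370 + 0.582)² / 0.0225 ≈ 169.3, rounded up to 170.

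The total is 340, as stated, with power 80.2%. The calculation makes no allowance for untreated patients, so it does not depend on which sentence governs.

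**2. Can the two sets differ?** The sequence is catheter insertion, randomization, then cooling to the assigned target. The interval before cooling starts should be short, but it is not zero. The documents give no number of patients randomized but not treated, so everything below is illustrative.

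**3. Shift in one arm's event rate.** Assume 85 events in 170 patients, and that k patients, all with events, are dropped from that arm:

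- k = 1: 84/169 − 0.5 = −0.30 percentage points
- k = 2: 83/168 − 0.5 = −0.60 points
- k = 5: 80/165 − 0.5 = −1.52 points

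**4. Type I error.** Assume 170 per arm and a true rate of 50% in both. Enumerate both binomial counts, remove k event patients, and apply the uncorrected chi-square test at two-sided 5%. Nothing in the method is specific to 31°C: dropping the same number from the 34°C arm gives the mirror image.

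| Dropped (31°C, 34°C) | Favours 31°C | Favours 34°C | Two-sided |
|---|---|---|---|
| 0, 0 | 2.30% | 2.30% | 4.59% |
| 1, 1 | 2.48% | 2.48% | 4.96% |
| 1, 0 | 2.88% | 2.23% | 5.11% |
| 2, 0 | 3.21% | 1.89% | 5.10% |
| 5, 0 | 4.66% | 1.30% | 5.96% |

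Part of the rise from 4.59% is discreteness of the test. To remove that, divide the shift in step 3 by √[0.25·(1/(170−k) + 1/170)]. The z shifts are 0, −0.054, −0.109 and −0.277 for k = 0, 1, 2 and 5, and the two-sided error is 5.00%, 5.03%, 5.14% and 5.89%.

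**5. Power.** If the same share is excluded from both arms and the rates stay at 50% and 35%, power is 79.8% at 1%, 79.4% at 2% and 78.1% at 5%. If everyone is analysed and that share of the moderate arm has the control rate, power is 79.3%, 78.5% and 75.9%.

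**6. A borderline table.** 85/170 against 68/170 events gives chi-square 3.43, p = 0.064. Dropping two early deaths from the moderate arm gives 66/168, chi-square 3.92, p = 0.048. The table was chosen to lie near the threshold. It shows that the choice of set could decide a close result, not that it is likely to.

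**The case against.** The strongest reply is that there is no real conflict. The clause in section 7.2 is set off by commas, which in ordinary usage describes the participants and does not select among them. The same sentence keeps patients in their randomized group and calls this intention to treat. Section 7 requires intention to treat for the primary outcome, section 8.1 names all randomized patients without qualification, section 7.3 also speaks of patients randomized, and no modified or per-protocol set is planned anywhere. This stands as evidence of intent: all randomized patients is the more likely meaning. It does not settle the text. If the clause merely describes, deleting it loses nothing; if it is a condition, it contradicts section 8.1.

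A second reply is that hardly anyone would be affected. Patients are excluded when the device is unavailable, allocation comes directly after the catheter is in place, and a patient with the catheter in place might be counted as treated. That is fair, and it limits the size of the problem.

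A third reply is that losses in one arm only have no obvious mechanism, since failure to start comes before the temperatures separate and the treating physician is blinded. This also largely stands. Similar losses in both arms are the more natural case, and one from each arm gives 4.96%. One-sided loss cannot be wholly excluded, because the bedside nurse who operates the device knows the allocation. The one-arm rows are therefore a bound under assumptions, not a forecast.

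**Conclusion.** The concern holds, as a minor point. Section 7.2, which sets the rule for the efficacy analysis, contains words that can be read as excluding randomized patients; section 8.1 includes them all, and no text ranks the two. The expected effect is small: for one or two event patients lost from one arm, the event rate moves by 0.3 or 0.6 percentage points and the type I error stays close to 5%. It reaches about 6% only if five are lost from one arm and none from the other. These figures assume 50% events in both arms and that every dropped patient had an event; the number dropped is an assumption throughout. No stated figure is wrong, and N = 340 stands. Confidence is high that the wording conflicts on the restrictive reading. There is no evidence that the trial intended to drop anyone.

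**What to change.** In section 7.2, delete the clause about receiving study treatment and insert the word *randomized*, so that the sentence begins *All randomized participants* and otherwise stays as it is. It then agrees with section 8.1 and with the baseline set in section 7.3. If a treated-only analysis is ever wanted, label it secondary and define what counts as treated before the data are seen; none is planned now, so this is optional. The cost is rewording one clause, with no added patients, data or analyses.
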